6.3.2. Caffeine, Alcohol, and Tobacco

- During each dosing session, participants will abstain from ingesting caffeine- or xanthine-containing products (e.g., coffee, tea, cola drinks and chocolate) for 24 h prior to the start of dosing until the participants leave the clinical unit.
- During each dosing session, participants will abstain from alcohol for 24 h prior to the start of dosing until the participants leave the clinical unit.
- For healthy participants, use of tobacco products is not allowed from screening until after participants leave the clinical unit.
- Participants with COPD who use tobacco products will be instructed that use of nicotine-containing products (including nicotine patches) will not be permitted while they are in the Clinical Unit. Participants with COPD will be escorted by staff for smoking breaks except during the period for 2 h prior to dosing and until all assessments are complete for 4 h after dosing.

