23. Positive Hepatitis C RNA test result at screening or within 3 months prior to first dose of study treatment

NOTE: Test is optional and participants with negative Hepatitis C antibody test are not required to also undergo Hepatitis C RNA testing

- 24. Positive pre-study drug/alcohol screen
- 25. Positive human immunodeficiency virus (HIV) antibody test
- 26. Regular use of known drugs of abuse

Other Exclusions

- 27. Male partners of women who are pregnant or lactating
- 28. Regular alcohol consumption within 3 months prior to the study defined as:
 - an average weekly intake of >21 units for males or >14 units for females. One unit is equivalent to 8 g of alcohol: a half-pint (~240 ml) of beer, 1 glass (125 ml) of wine or 1 (25 ml) measure of spirits.
- 29. Unable to refrain from smoking for 2 h prior to dosing and until all assessments are complete for 4 h after dosing and also for 1 h prior to any vital signs and ECG assessments.

- 30. History of sensitivity to any of the study medications, including CCI15106 or components thereof and, for cohorts that will undergo BAL, those that may be used in association with the BAL procedure or components thereof or a history of drug or other allergy that, in the opinion of the investigator or Medical Monitor, contraindicates their participation.
- 31. For cohorts that will undergo BAL, contraindications to bronchoalveolar lavage including hypercapnia >50 mm Hg, abnormal blood coagulation parameters, known or suspected intolerance of medications necessary for bronchoscopy, refractory hypoxemia, reactive airway disease or asthma, unstable angina or acute myocardial infarction.
- 32. Documented lactose allergy/intolerance.

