- 6. To be performed at the following timepoints in the mornings only: pre-dose, and 0.25, 0.5, 1, 4 h post-dose
- 7. To be performed at the following timepoints in the mornings only: pre-dose and 4 h post-dose
- 8. ECG and vital signs to be obtained 2 h after the morning dose
- 9. BID

2016N290366_02 **CONFIDENTIAL**

10. PK samples on days 1, 3, 6, and 19 will be collected at the following timepoints: pre-dose, 0.25, 0.5, 0.75, 1, 2, 4, 6, 8, 10, 12 h. On day 2, one sample in the morning (24h post day 1 dose). On days 4 and 5, one sample on each morning (24h and 48h post day 3 dose). On days 6 and 19, the evening dose will be given after 12 h post-dose sample is collected. On all other days, PK sample will be collected once, before the morning dose (if on dosing days).

205822

Schedule for Cohort A Part 2 (and all other single dose administrations)

				Т	reatme	nt Period	, Days	(D) and	l hours (h)							
	D-1						D.	1									
Procedure		Pre- dose	0h	0.25h	0.5h	0.75h	1h	2h	4h	6h	8h	10h	12h	24h			
Inclusion and exclusion criteria	Х																
Brief physical examination, oral examination	Х													Χ			
Substance testing (drugs, alcohol)	Х																
Serum pregnancy test in women	Х																
Admittance to clinic	Х																
Inhaler device training ¹	Х																
Randomization	X2																
Discharge														X3			
Haematology, clinical chem and urinalysis (include liver chem) ⁴	Х													Χ			
Spirometry		X ⁵		X ⁶	Χ		X6		X ₆								
Telemetry			30 r	nin pre-d		d continu		il at lea	st 4 h								
12-lead ECG and vital signs		XXX		Х			Χ	Χ	Х		Χ		Χ				
CCI15106-IP or placebo treatment			Χ														
PK blood sample ⁷		Х		Х	Χ	Х	Χ	Χ	Х	Χ	Χ	Χ	Χ	Χ			
AE review		← =	=====	======	=====	=====	=====	=====	=====	=====	=====	=====	=====	\rightarrow			
SAE review	←====	=====			=====			=====	=====		=====		=====	==>			
Concomitant medication review	←====	=====			=====				=====		=====		=====	==>			

- 1. Day -1 inhaler training may be done on Day 1 instead, before the first dose administration. Other time-points may be added per investigators discretion
- 2. Can be performed on Day 1 prior to dosing
- 3. After all assessments are completed
- 4. To be drawn fasting (for at least 8 h)
- 5. To be performed within 15 to 60 minutes pre-dose
- 6. To be performed after ECG, VS and PK blood draw are obtained
- 7. Additional PK collection time points may be added to better characterize the PK profile

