Repeat dose schedule to be followed for repeat dose cohorts in Parts 1 and 2 (other than Cohort A Part 1)

Procedure	Treatment Period, Days															
	-1	1	2	3	4	5	6	7	8	9	10	11	12	13	14	15
Inclusion and exclusion criteria	Х															
Brief physical examination, oral examination	Х															Χ
Substance testing (drugs, alcohol, tobacco1)	Х															
Inhaler device training ²	Х															
Serum pregnancy test in women	Х															
Admittance to clinic	Х															
Randomization	X3															
Discharge																X ⁴
Dosing procedure training with bystanders		X 5														
Haematology, clinical chem and urinalysis (include liver chem) ⁶	Х							Χ								Χ
Spirometry		X ⁷		X8			X8					X8			X ⁷	
Telemetry (starting 30 min pre-morning dose and continuous at least 4h post-morning dose)		Х						Х						X9		
12-lead ECG and vital signs ¹⁰	XXX	Χ		Х	Χ		Х	Χ	Х		X11		X11			
CCI15106-IP or placebo treatment BID, device incident assessment BID ¹²		Х	Х	Х	Х	Х	Х	Х	Х	Х	Х	Х	Х	Х	Х	
PK blood sample ¹³		Χ	Χ		Χ		Χ		Χ		Χ		Χ		Χ	Χ
BAL	X14															
Urea blood sample	X15															
AE review	←========→															
SAE review	←======== →					\rightarrow										
Concomitant medication review	←						\rightarrow									

- 1. Tobacco test to be performed only in healthy participants
- 2. Day -1 inhaler training may be done on Day 1 instead, before the first dose administration. Other time-points may be added per investigators discretion.
- 3. Can be performed on Day 1 prior to dosing
- 4. After all procedures and assessments are complete
- 5. To be done only in Cohort(s) where bystanders are present. Can be performed on Day -1 instead, if desired. Other time-points may be added per investigators discretion.
- 6. To be drawn fasting (for at least 8 h)
- 7. To be performed at the following timepoints in the mornings only: pre-dose, and 0.25 (in participants with COPD only), 0.5, 1, 4 h post-dose
- 8. To be performed at the following timepoints in the mornings only: pre-dose and 4 h post-dose

2016N290366_02 **CONFIDENTIAL** 205822

- 9. Telemetry may be performed on Days 11 or 12 instead, not to coincide with the BAL procedure.
- 10. ECG and vital signs to be obtained 2 h after the morning dose
- 11. When BAL is performed, vital signs and ECG will be performed before and after the procedure and oxygen saturation will be measured continuously.
- 12. For cohort with bystanders, BID doses may have ± 1.5 h window.

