6.3.2. Caffeine, Alcohol, and Tobacco

- During each dosing session, participants will abstain from ingesting caffeine- or xanthine-containing products (e.g., coffee, tea, cola drinks and chocolate) for 24 h prior to the start of dosing until the participants leave the clinical unit.
- During each dosing session, participants will abstain from alcohol for 24 h prior to the start of dosing until the participants leave the clinical unit.
- For healthy participants, use of tobacco products is not allowed from screening until after participants leave the clinical unit.
- Participants with COPD who use tobacco products will be instructed that use of
 nicotine-containing products (including nicotine patches) will not be permitted while
 they are in the Clinical Unit. Participants with COPD will be escorted by staff for
 smoking breaks except during the period for 2 h prior to dosing and until all
 assessments are complete for 4 h after dosing.

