9. STUDY ASSESSMENTS AND PROCEDURES

- Study procedures and their timing are summarized in the SoA (Section 2).
- Protocol waivers or exemptions are not allowed
- Immediate safety concerns should be discussed with the sponsor immediately upon occurrence or awareness to determine if the participant should continue or discontinue study treatment.
- Adherence to the study design requirements, including those specified in the SoA (Section 2), is essential and required for study conduct.
- All screening evaluations must be completed and reviewed to confirm that potential
 participants meet all eligibility criteria. The investigator will maintain a screening
 log to record details of all participants screened and to confirm eligibility or record
 reasons for screening failure, as applicable.
- Procedures conducted as part of the participant's routine clinical management (eg, blood count) and obtained before signing of ICF may be utilized for screening or baseline purposes provided the procedure met the protocol-specified criteria and was performed within the time frame defined in the SoA (Section 2).
- The maximum amount of blood collected from each participant over the duration of the study, including any extra assessments that may be required, will not exceed 500 mL.
- Repeat or unscheduled samples may be taken for safety reasons or for technical issues with the samples.
- The following time window tolerances apply to all protocol assessments:

Predose	- 60 to 0 min (- 60 to -15 min for spirometry)
0h - 4h post	- 5 / + 10 min
5h – 24h post	- 20 / + 20 min

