10.3. Statistical Analyses

The analysis and reporting of Part 1 may be conducted prior to the completion of Part 2. For all parts, the analysis and reporting will be performed after the datasets are authorized and released for reporting.

Data will be listed and summarized according to GSK reporting standards, where applicable. Listings will be sorted by cohort, participant and time; summaries will be presented by cohort, treatment, and time.

Descriptive summaries will include n, mean, standard deviation (SD), median, minimum, and maximum, geometric mean with associated 95% confidence interval (CI), and the between-participant coefficient of variation (%CVb) for continuous variables, n and percent will be used as summary statistics for categorical variables.

Baseline or pre-dose assessment is the last available assessment prior to time of the first dose unless it is specified otherwise. If there are multiple assessments collected at the same scheduled time, the average of these assessments will be used. For tabulated safety summaries, only the scheduled assessments will be included in the summary tables.

Version 9.1 or higher of the SAS system will be used to analyze the data as well as to generate tables, figures, and listings.

Complete details will be documented in the RAP.

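### The smoking-break rule for COPD participants omits the 1 h abstinence before ECG and vital signs that exclusion criterion 28 presumes, leaving the Part 2 Cohort B baseline and, separately, the Part 2 Cohort A 8 h and 12 h readings unprotected

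*Protocol*

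**What the plan says.** Section 6.3.2 (same wording in the current amendment and both earlier versions) sets the rule that staff apply during confinement: "Participants with COPD will be escorted by staff for smoking breaks except during the period for 2 h prior to dosing", the barred period ending when "assessments are complete for 4 h after dosing". It says nothing about ECG or vital-sign times.

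Section 6.2.2, criterion 28 in the current amendment (29 in the two earlier versions), excludes anyone unable to abstain over the same dosing window "and also for 1 h prior to any vital signs and ECG assessments". Current smokers are eligible, as are ex-smokers (Section 6.1.2, criterion 4).

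The readings are placed in Section 2:

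- **Part 2 Cohort B (repeat-dose schedule):** triplicate ECG and vital signs on Day -1, then Days 1, 3, 4, 6, 7, 8, 10 and 12, with "ECG and vital signs to be obtained 2 h after the morning dose".
- **Part 2 Cohort A ("Schedule for Cohort A Part 2 (and all other single dose administrations"):** triplicate pre-dose on Day 1, then 0.25, 1, 2, 4, 8 and 12 h.

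Section 10.3 defines baseline: "Baseline or pre-dose assessment is the last available assessment prior to time of the first dose unless it is specified otherwise". Section 10.3.1 tabulates change from baseline for ECG and vital signs, and Section 8.1.2 has a withdrawal rule on a QTc change from baseline above 60 msec.

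**The concern.** The eligibility criterion and the conduct rule describe different abstinence periods. Someone escorting breaks will follow 6.3.2, and a break shortly before the Day -1 ECG complies with it. The hour that criterion 28 treats as worth protecting is thus protected for some readings and open for others, and the split falls between baseline and on-treatment values within each COPD cohort.

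ECG and vital signs are primary safety endpoints, summarised as change from baseline. If smoking raises heart rate or blood pressure (the documents do not say so, but the 1 h condition suggests that an effect on these readings was foreseen), a post-cigarette baseline compared with smoke-free on-treatment values understates a rise. A smoke-free baseline compared with post-cigarette values overstates one. Placebo participants are exposed in the same way, but there are only two in each cohort, too few to measure the artefact and remove it. The protocol does not ask for smoking times to be recorded, so it could not be adjusted for afterwards either.

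**Working it through.** The plan gives no figure on this point, so there is nothing to reproduce. The check is whether the 60 minutes before each scheduled reading fall inside the period barred by 6.3.2.

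**Inputs**

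- Barred period, in minutes from the morning dose: start -120; end +240, or +250 when the 4 h assessments are taken at the late limit (Section 6.3.2; +10 min tolerance in Section 9).
- Time tolerances (Section 9, current amendment): pre-dose "60 to 0 min (- 60 to -15 min for spirometry"); 0 to 4 h, -5/+10 min; 5 to 24 h, -20/+20 min.
- Reading times: Section 2, as listed above.

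**Rule:** a reading is protected if (earliest time - 60) is at or after -120 and its latest time is at or before +250.

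| Reading | Cohort (Part 2) | Earliest - 60 | Latest | Minutes open to smoking, nominal time |
|---|---|---|---|---|
| Day -1 triplicate | B (baseline) | no dose that day | – | 60 of 60 |
| Day 1 pre-dose | A (baseline) | -60 - 60 = -120 | 0 | 0 |
| 0.25 h | A | 15 - 5 - 60 = -50 | 25 | 0 |
| 1 h | A | 60 - 5 - 60 = -5 | 70 | 0 |
| 2 h | A and B | 120 - 5 - 60 = 55 | 130 | 0 |
| 4 h | A | 240 - 5 - 60 = 175 | 250 | 0 |
| 8 h | A | 480 - 20 - 60 = 400 | 500 | 60 of 60 |
| 12 h | A | 720 - 20 - 60 = 640 | 740 | 60 of 60 |

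**Cohort B.** The Day -1 triplicate is the last scheduled ECG and vital-sign assessment before the first dose, because the Day 1 reading is at 2 h. It is therefore the baseline under Section 10.3. No dose is given on Day -1, so 6.3.2 bars no break before it. The 2 h on-treatment readings follow 120 + 120 = 240 minutes of barred time at the nominal hour.

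**Cohort A.** The pre-dose baseline just fits, since its earliest preceding hour starts exactly at the 2 h limit. The 8 h and 12 h readings lie wholly outside the barred period, and this cohort has no evening dose to start a new one.

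**Is the 1 h condition supplied elsewhere?** Section 9.4.3 (vital signs) and Section 9.4.4 (ECG) ask for 5 minutes' rest. The schedules are silent on smoking before readings. The only other smoking note bearing on a measurement is an Appendix 4 footnote on oral temperature for fever grading. So it is not supplied.

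**The case against.** The best reply is that the condition is already in the protocol. Criterion 28 makes little sense unless participants are expected to abstain for that hour, 6.3.2 does not state that smoking is allowed then, and staff who escort every break can satisfy both texts. That is fair as far as it goes: the two are not logically incompatible, and a careful site may apply the 1 h condition anyway. But the criterion tests ability to abstain; it does not tell anyone to do so, and the section that governs breaks names one exception and leaves the rest open.

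A second reply is that detection does not rest on change from baseline alone. This stands. The QTc limit of 500 msec, the absolute heart-rate and blood-pressure grades, the investigator's ECG and telemetry judgements and adverse-event reporting do not use the Day -1 value. In Cohort A the readings around the predicted plasma peak (about 15 min) are protected, and summaries are presented by time, so any effect stays in the 8 h and 12 h rows.

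Several stronger readings are tempting and should be resisted:

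- *All Cohort B change values are distorted.* A reader might count 8 days x 14 participants = 112 values, and 2 times x 8 participants = 16 of 48 in Cohort A. These are scheduled values. Ex-smokers cannot be affected, nor can a smoker who took no break in that hour.
- *A bias in beats per minute can be stated.* The documents give neither the share of current smokers nor the size of a smoking effect, and multiplying two assumed figures would also require every smoker to smoke just before the reading. The lower bound is zero.
- *The two cohorts are biased in opposite directions.* The rule permits this; nothing shows that it happens.
- *6.3.2 contradicts itself by banning nicotine in the unit and providing breaks.* Escorted breaks are plausibly taken outside the unit, so the text does not establish a contradiction.

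**Conclusion.** The omission is real and persists in the current amendment. It has two separate consequences in Part 2. In Cohort B (12 active, 2 placebo) the baseline is unprotected and the routine on-treatment readings are protected, so a rise from baseline could be masked; the QTc change-from-baseline withdrawal rule uses the same baseline. In Cohort A (6 active, 2 placebo) the baseline is protected and the 8 h and 12 h readings are not, so a rise could be mimicked at those two times. The exposed readings do not form one series: Cohort B has no 8 h or 12 h ECG in its schedule, and Cohort A does not use Day -1 as baseline.

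The size is known only as opportunity: 60 of 60 minutes open before each exposed reading, none before the other readings checked. The effect on the data depends on how many participants currently smoke, whether they take a break in that hour, and how much a cigarette moves the reading. The documents give none of these, and the effect may be zero. The direction rests on the assumption that smoking raises the measured value. The point is still worth acting on, because the protocol's own eligibility criterion treats that hour as relevant and the artefact is avoidable.

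**What to change.** Reconcile Section 6.3.2 with criterion 28 by adding the condition the criterion already contains: no escorted smoking break within 1 h before a scheduled in-unit vital-sign or ECG assessment, including the Day -1 baseline and the 8 h and 12 h readings. This takes the time that the break rule leaves open before those readings from 60 minutes to 0 and leaves the other readings as they are.

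The cost is one sentence and some delayed breaks; breaks are already escorted, so they only need timing. The change concerns confinement only. It does not reach the follow-up visit, or a cigarette smoked before admission on Day -1 if the triplicate is taken within an hour of arrival.

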6.3.3. Activity

• Participants will abstain from strenuous exercise from screening until follow-up visit. Participants may participate in light recreational activities during studies (eg, watching television, reading).

6.4. Screen Failures

Screen failures are defined as participants who consent to participate in the clinical study but are not subsequently randomized. A minimal set of screen failure information is required to ensure transparent reporting of screen failure participants to meet the Consolidated Standards of Reporting Trials (CONSORT) publishing requirements and to respond to queries from regulatory authorities. Minimal information includes demography, screen failure details, eligibility criteria, and any SAEs.

Individuals who do not meet the criteria for participation in this study may be rescreened only upon approval of Medical Monitor. Rescreened participants should be assigned a different screening number.

7. TREATMENTS

Study treatment is defined as any investigational treatment(s), marketed product(s), placebo, or medical device(s) intended to be administered to a study participant according to the study protocol.

7.1. Treatments Administered

Study Treatment Name:	CCI15106-IP	Placebo
Dosage formulation:	1 capsule	1 capsule
Unit dose strength(s)/Dosage level(s): Route of Administration	30 mg of CCI15106 As 30.3 mg of CCI15106: polyvinyl alcohol 99:1 w/w PRINT 0.9x1 µm cylinder shape crystalline particles By inhalation	30.3 mg of lactose: polyvinyl alcohol 98:2 w/w PRINT 0.9x1 μm cylinder shape amorphous particles By inhalation
Dosing instructions:	Each inhalation will follow instructions provided with the device. The number of inhalations will depend on the dose. The morning dose to be taken fasting (at least 8 h). For repeat dose cohorts, the evening dose to be taken at least 2 h after food. For repeat dose cohort(s) with bystander exposure monitoring, a ±1.5 h window is allowed.	Each inhalation will follow instructions provided with the device. The number of inhalations will depend on the dose. The morning dose to be taken fasting (at least 8 h). For repeat dose cohorts, the evening dose to be taken at least 2 h after food. For repeat dose cohorts with bystander exposure monitoring, a ±1.5 h window is allowed.
Packaging and Labeling	Study Treatment will be provided in a HDPE (high density polyethylene) bottle. Each bottle contains 2 capsules and a desiccant canister. Each bottle is overwrapped in a foil pouch containing a desiccant sachet. Each bottle and each pouch will be labelled as required per country requirement.	Study Treatment will be provided in a HDPE bottle. Each bottle contains 2 capsules and a desiccant canister. Each bottle is overwrapped in a foil pouch containing a desiccant sachet. Each bottle and each pouch will be labelled as required per country requirement.
Device	Monodose RS01	Monodose RS01
Manufacturer	Plastiape S.p.A.	Plastiape S.p.A.

7.1.1. Medical Devices

- The GSK manufactured medical devices (or devices manufactured for GSK by a third party) provided for use in this study are Monodose RS01.
- Instructions for medical device use are provided in the Study Reference Manual (SRM).
- GSK medical device incidents, including those resulting from malfunctions of the device, must be detected, documented, and reported by the investigator throughout the study (see Section 9.2).

7.2. Dose Modification

- This protocol allows some alteration from the currently outlined dosing schedule. The maximum daily dose administered will not exceed 120 mg per day either as a single dose or as 60 mg BID.
- The decision to proceed to Part 1 Cohort B will be made by the GSK Study Team comprised at a minimum of the team leader, medical monitor, Global Clinical Safety and Pharmacovigilance scientist or physician (Clinical Pharmacokineticist, Statistician and Preclinical Safety Assessment as necessary), and the Investigator or delegate based on safety and tolerability data obtained in all participants at the prior dose levels in Part 1. The actual doses to be administered may be adjusted based on safety, tolerability, and preliminary PK data if appropriate, at previous dose levels; these dose adjustments may involve either an increase or a decrease in the planned dose. The highest dose in the study will not exceed 120 mg per day either as a single dose or as 60 mg BID.
- The decision to proceed to participants with COPD will be made by the GSK Study Team comprised at a minimum of the team leader, medical monitor, Global Clinical Safety and Pharmacovigilance scientist or physician (Clinical Pharmacokineticist, Statistician and Preclinical Safety Assessment as necessary), and the Investigator or delegate based on safety and tolerability data obtained after single dosing completes in healthy participants in Part 1 Cohort A.
- The actual doses to be administered may be adjusted based on safety, tolerability, and preliminary PK data if appropriate, at previous dose levels; these dose adjustments may involve either an increase or a decrease in the planned dose.
- The dosing schedule may also be adjusted to expand a dosing cohort to further evaluate safety and PK findings at a given dose level, or to add cohorts to evaluate additional dose levels. The study procedures for these additional participant(s) or cohort(s) will be the same as that described for other study participants.

